### Prohibited concomitant medications

Concurrent therapy with a marketed or investigational anticancer therapeutic or radiation to large marrow reserves for either a palliative or therapeutic intent is excluded. Short-term corticosteroids for non-malignant conditions (e.g. asthma, inflammatory bowel disease) equivalent to a Dexamethasone dose > 4.0 mg/day or Prednisone 100 mg per day are not permitted. Higher steroid doses given short term for exacerbations of nonmalignant conditions (e.g. asthma flare) are permitted with the approval of the coordinating investigator. Investigational agents are not to be used during the study.

### Minor Surgical Procedures

For minor procedures (such as a central line placement, needle biopsy, thoracentesis, or paracentesis) lbrutinib should be held for at least 3 days prior to the procedure and should not be restarted for at least 3 days after the procedure. For bone marrow biopsies that are performed while the patient is on lbrutinib, it is not necessary to hold study drug for these procedures.

#### Major Surgical Procedures

For any surgery or invasive procedure requiring sutures or staples for closure, Ibrutinib should be held at least 7 days prior to the intervention and should be held at least 7 days after the procedure and restarted at the discretion of the investigator when the surgical site is reasonably healed without serosanguinous drainage or the need for drainage tubes.

#### **Emergency Procedures**

For emergency procedures, study drug should be held after the procedure for at least 7 days after the urgent surgical procedure.

## 11.4 Other Protocol-required Therapies

All other protocol-required therapies listed below are commercially available and will not be provided or reimbursed by the sponsor. The investigator will be responsible for obtaining supplies of these treatment-required therapies.

## 11.4.1 Antiviral prophylaxis

An antiviral concomitant medication is required for the duration of treatment with Carfilzomib. Acyclovir (e.g. 400 mg p.o. 3 times a day, or 800 mg p.o. 2 times a day or per institutional standards), Famcyclovir (e.g. 125 mg p.o. given 3 days, twice a day or per institutional standards), or Valacylovir (e.g. 500 mg p.o., twice a day or per institutional standards). Dose adjustments for renal function where appropriate (see section 11.3.2.1), initiated within 1 week of the first dose, should continue for the duration of treatment with Carfilzomib.

Hepatitis B prophylaxis has to be initiated in patients which are positive for either HBsAg and / or anti-HBc and HBV-DNA negative. Prophylaxis treatment is in the discretion of the treating investigator and could be include Entecavir, Tenofir or other substances preventing HBV reactivation. HBV-DNA needs to be re-evaluated in regular intervals (for more details see section 12.4.12.9).

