 Cycle 1 (day 1-28)\* 20mg/m^2 i.v. day 1

70 mg/m  i.v. day 8, 15 of a 28 days cycle
Cycle 2-12 (28-day cycles)*
70mg/m  i.v. day 1, 8, 15 of a 28 days cycle
Cycle 13-24 (28-day cycles)*
70mg/m  i.v. day 1, 15 of a 28 days cycle

\*Prophylaxis for HZV reactivation is obligatory for all patients treated with Carfilzomib during the treatment phase. Acceptable antiviral therapy includes acyclovir (e.g. 400mg p.o. 3 times-a-day), famcyclovir (e.g. 125mg p.o. twice-a-day) or valacyclovir (e.g. 500mg p.o. twice-a-day). Prophylactic Dexamethasone (4 mg) is obligatory before the first Carfilzomib infusion and for later Carfilzomib infusions as indicated.

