total of 120 applications of 36 mg/m^2 each, summing up to 4320 mg/m^2 per patient. In the second trial patients received escalating doses up to 45 mg/m^2 6 applications for the first 12 cycles (n=72 applications) and later on 4 applications up to 45 mg/m^2, resulting in a higher cumulative dose per patient compared to the multiple myeloma trial. Of note, both trials did not find a dose limiting toxicity as mentioned above. In our trial Carfilzomib will be given with a starting dose of 20 mg/m^2 on day 1 cycle 1, and if tolerated, the dose will be increased to 70 mg/m^2 for day 8 and 15 of cycle 1 (n = 3 applications). Carfilzomib will be administered thereafter on day 1, 8, 15 of cycle 2 to 12 (n = 33 applications) and on day 1 and 15 for cycle 13 to 24 (n = 24applications). In summary the patients will receive 4150 mg/m^2 Carfilzomib in this trial. Thus, our trial will combine Ibrutinib at lower dose with a total amount of Carfilzomib comparable to the both studies described above. We do not use the twice weekly application of Carfilzomib at a dose of 56 mg/m^2, but the once weekly application of Carfilzomib at 70 mg/m^2. This not only reduces the total amount of Carfilzomib given per week, but there are in addition large data sets in patients with multiple myeloma, demonstrating convincingly that the toxicity of the once weekly application is not higher, but probably even lower than the twice weekly application with comparable efficacy. This was demonstrated in several large phase III trials and is summarized in the publication by Moreau et al. In this pooled analysis the authors state that "In the sideby-side analysis of the subgroups, fewer grade  $\geq$  3 AEs were observed with Kd70 QW (67.6%) compared with Kd56 BIW (85.3%), despite similar median treatment exposure times (38.1 vs 40.3 weeks). The frequency of grade  $\geq$  3 AEs of interest also differed between Kd70 QW and Kd56 BIW, with lower rates of cardiac failure (1.4% vs 5.1%), acute renal failure (3.4% vs 6.0%), and hypertension (5.5% vs 15.7%) observed with Kd70 QW vs Kd56 BIW. In a safety analysis limited to the first 6 months from receiving treatment, a lower frequency of grade  $\geq$  3 AEs with Kd70 QW vs Kd56 BIW was also observed. These results support that Kd70 QW represents a convenient and well-tolerated dosing option for patients with RRMM." Based on the data of the ENDEAVOUR trial Carfilzomib one weekly at 70 mg/m^2 was already approved earlier on by the FDA and EMA for multiple myeloma.

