## 11.1 Experimental arm (arm A)

Treatment with Ibrutinib will be given until evidence of progressive disease or if the patient didn't tolerate the therapy anymore (maximum of 7 years' treatment within the study after first patient in). Additionally, all patients in arm A receive Carfilzomib for two years. Treatment courses are administered in 28-day cycles. If one drug has been discontinued due to toxicities, the other drug can be administered alone in arm A according the protocol.

Cycle 1			
Ibrutinib	420 mg p o	Daily, until evidence of progressive disease or no	
420 mg p.o.		longer tolerated by the patient	
Carfilmarnih 20 mg/m  i.v.		Day 1	
Carnizonnio	70 mg/m² i.v.	Day 8,15	
Cycle 2-12			
Ibrutinib	420 mg p.o.	Daily, until evidence of progressive disease or no	
		longer tolerated by the patient	
Carfilzomib	70 mg/m  i.v.	Day 1,8,15	
Cycle 13-24			
Ibrutinib 420 mg n o		Daily, until evidence of progressive disease or no	
	420 mg p.0.	longer tolerated by the patient	
Carfilzomib	70 mg/m  i.v.	Day 1,15	
From Cycle 25 until end of treatment			
Ibrutinib	420 mg p.o.	Daily, until evidence of progressive disease or no	
		longer tolerated by the patient	

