## **11.3.2 Dose modifications for Carfilzomib**

# 11.3.2.1 Dosage adjustments, delays, rules for withholding or restarting, permanent discontinuation

Carfilzomib will be discontinued, temporarily delayed, or dosage temporarily reduced, in the event of a treatment-related adverse event that, in the opinion of the investigator, warrants the discontinuation, temporary delay or dose reduction, as indicated in Table 5 and Table 6. The patient will be considered on protocol treatment while receiving either Carfilzomib and / or lbrutinib (i.e. if either Carfilzomib or lbrutinib are discontinued or interrupted, the patient is still considered on treatment if still taking the other investigational product). If day 1 of a cycle is delayed, day 1 of subsequent cycles should be adjusted accordingly to maintain the 28-day cycle duration. However, if a within-cycle dose is delayed, then the dates of the subsequent within-cycle doses should not be adjusted. If Carfilzomib administration does not commence

within the allowable window of the scheduled administration date, then this dose will be considered a missed dose with continuation of the subsequent cycles. Administration may resume at the next planned dosing date. A missed dose will not be made up. Carfilzomib must be discontinued permanently if a delay of more than 6 weeks is required due to unresolved toxicity.

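### Section 11.4.1 gives a three-day famciclovir example for an antiviral that must cover the whole of carfilzomib treatment

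*Protocol*

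**What the plan says.** Protocol section 11.4.1 opens with the rule: "An antiviral concomitant medication is required for the duration of treatment with Carfilzomib". It then offers three drugs as examples. Aciclovir and valaciclovir are given as a dose and a daily frequency. The famciclovir entry adds a number of days: "Famcyclovir (e.g. 125 mg p.o. given 3 days, twice a day or per institutional standards".

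The Arm A text in the synopsis (section 5) makes the same requirement in stronger terms, "Prophylaxis for HZV reactivation is obligatory for all patients treated with Carfilzomib during the treatment phase", and lists famciclovir with no day limit: "famcyclovir (e.g. 125mg p.o. twice-a-day".

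On the length of carfilzomib treatment, section 11.1 says "Additionally, all patients in arm A receive Carfilzomib for two years". Section 7.6.3 places the later infusions "on day 1 and 15 for cycle 13 to 24".

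The last sentence of the antiviral paragraph in 11.4.1 begins "Dose adjustments for renal function where appropriate (see section 11.3.2.1), initiated within 1 week of the first dose" and goes on to require continuation for as long as carfilzomib is given. The section it refers to opens with "Carfilzomib will be discontinued, temporarily delayed, or dosage temporarily reduced, in the event of a treatment-related adverse event" and deals with holding, delaying and stopping carfilzomib.

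**The concern.** A required medication and an example of how to give it should agree. Here the rule covers the whole of carfilzomib treatment, while one of the three examples, read as written, ends after three days. A site that took the famciclovir entry literally would leave a patient without herpes zoster prophylaxis for almost all of the carfilzomib schedule.

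The protocol treats this prophylaxis as a safety requirement. Section 10.3 excludes patients with a contraindication to the required concomitant drugs and names hypersensitivity to antivirals. Section 11.4 leaves it to the investigator to obtain these drugs, so this paragraph is the protocol's detailed dosing guidance to sites.

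The sentence that should restate the rule is also faulty. As constructed, its start time and duration belong to the renal dose adjustment and not to the prophylaxis, and its cross-reference leads to a section with no renal or antiviral rule. It therefore does little to correct the example. These two faults are editorial and do not raise the weight of the point.

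**Working it through.** The protocol has no figure of its own to reproduce here. The check is a comparison of texts, followed by simple arithmetic for scale.

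**Texts side by side**

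| Place | Content | Day limit |
|---|---|---|
| 11.4.1, opening rule | antiviral required | none; whole of carfilzomib treatment |
| 11.4.1, aciclovir | 400 mg three times a day or 800 mg twice a day, or institutional standard | none |
| 11.4.1, famciclovir | 125 mg twice a day, or institutional standard | **3 days** |
| 11.4.1, valaciclovir | 500 mg twice a day, or institutional standard | none |
| Synopsis, rule | prophylaxis obligatory | none; treatment phase |
| Synopsis, famciclovir | 125 mg twice a day | none |

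The famciclovir entry in 11.4.1 is the only one with a day limit. It conflicts with the rule that opens its own paragraph and with the synopsis entry for the same drug and dose.

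**Length of cover required**

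Inputs: 24 cycles of 28 days, with infusions on days 1 and 15 in cycles 13 to 24 (sections 7.6.3, 11.1 and 11.3.1.1).

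- Last scheduled infusion, cycle 24 day 15: 23 × 28 + 15 = day 659.
- End of cycle 24: 24 × 28 = day 672.
- Cover if prophylaxis starts on day 1: days 1 to 659, or 659 days.
- Cover if it starts one week after the first dose: days 8 to 659, or 659 − 7 = 652 days.

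**The example read literally**

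- 3 days × 2 doses a day = 6 doses.
- Share of the period covered: 3/659 = 0.46%; 3/652 = 0.46%; 3/672 = 0.45%.

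**The cross-reference**

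Section 11.3.2.1 covers carfilzomib discontinuation, delay, reduction and missed doses. It contains no renal rule and no antiviral rule. Renal function appears in Table 7 of section 11.3.2.4, but those entries govern the carfilzomib dose only.

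**Timing**

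Section 9.1 gives last inclusion as Q2 2024. If a patient were included on 30 June 2024, started at once and had no delays, day 659 would be 30 June 2024 + 658 days = 19 April 2026.

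**The case against.** The strongest reply is that the instruction to sites is clear despite the slip. The full-duration rule opens the paragraph, its closing sentence mentions the same duration, and the synopsis calls prophylaxis obligatory. The faulty words sit in an illustrative parenthesis for one of three interchangeable drugs, and the same parenthesis allows institutional standards. To lose cover, a site would have to choose famciclovir, set aside its own standard, treat an example as a stop rule and override the opening sentence. On this view it is a proofreading note, and the percentage measures a reading that the surrounding text rules out.

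Much of this stands. A careful investigator would probably follow the rule, and no number of affected patients can be derived from the protocol. The percentage describes only the literal reading. The calendar date depends on its assumptions and does not show that anyone is still on carfilzomib.

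The reply does not remove the contradiction. The wrong duration stands in the operative dosing text for an obligatory safety medication, not in background material, and nothing is gained by leaving it there.

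One could also re-point the renal cross-reference to Table 7 instead of removing it. Since that table concerns carfilzomib and not the antivirals, re-pointing would not supply the missing rule.

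**Conclusion.** The inconsistency is real and is in the current text, but it is minor. The famciclovir example in 11.4.1 contradicts that section's own rule and the synopsis. Taken literally it would give 3 days of cover where 652 to 659 days are required, about 0.5%.

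That size is the worst case for one patient who completes all 24 cycles without delay at a site that follows the example as written. Stopping carfilzomib early shortens the period required. The full-duration rule itself is sound, and the trial design, sample size and primary analysis are not affected. The correction should be made.

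**What to change.** In section 11.4.1:

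1. Delete the three-day limit from the famciclovir example, so that it reads as in the synopsis: 125 mg by mouth twice a day, or per institutional standards.
2. Reword the last sentence of that paragraph so that the prophylaxis itself, not the renal adjustment, starts within one week of the first dose and continues for as long as carfilzomib is given.
3. Remove the reference to section 11.3.2.1.

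The cost is a wording change in one paragraph and a note to sites. Section 19.8 requires agreement by the coordinating investigator, both supporting companies and the sponsor, and ethics committee and competent authority approval or advice before implementation. The change should therefore go into the next amendment; a separate one for this point alone is not needed.

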## 11.4.2 Thromboprophylaxis

An anticoagulant (e.g. enteric-coated aspirin at standard prophylactic dose or other anticoagulant or antiplatelet medication such as clopidogrel bisulfate, low molecular weight heparin, or warfarin) is a suggested concomitant medication and should be used with caution in patients on Ibrutinib. Application in patients should be based on an individual benefit risk assessment at the discretion of the investigators.

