- Glucocorticoid therapy within 14 days prior to randomization that exceeds a cumulative dose of 160 mg of Dexamethasone or equivalent dose of other corticosteroids.
- Focal radiation therapy within 7 days prior to randomization. Radiation therapy to an extended field involving a significant volume of bone marrow within 21 days prior to randomization (i.e. prior radiation must have been to less than 30% of the bone marrow).
- Contraindication to any of the required concomitant drugs or supportive treatments, including hypersensitivity to antiviral drugs.
- Hypersensitivity to the active substances or to any of the excipients of the investigational medicinal products.
- Active infection within 14 days prior to randomization requiring systemic antibiotics, antiviral (except antiviral therapy directed at hepatitis B) or antifungal agents. Such infection must be fully resolved prior to randomization.
- Ascites requiring paracentesis within 14 days prior to randomization.
- Uncontrolled hypertension, defined as an average systolic blood pressure > 159 mmHg or diastolic > 99 mmHg despite optimal treatment (measured according European Society of Hypertension/European Society of Cardiology [ESH / ESC] 2013 guidelines.
- History of stroke or intracranial hemorrhage within 6 months prior to randomization.
- Known interstitial lung disease.
- Infiltrative pulmonary disease, known pulmonary hypertension.
- Known chronic obstructive pulmonary disease (COPD) with a forced expiratory volume in 1 second (FEV1) < 50% of predicted normal.

- Known severe persistent asthma within the past 2 vears (see also https://www.nhlbi.nih.gov/files/docs/guidelines/asthsumm.pdf), or currently has uncontrolled asthma of any classification or at time of screening has an FEV1 of < 50% of predicted normal.
- Autologous or allogeneic stem cell transplant less than 100 days prior to randomization.
- Vaccination with live attenuated vaccines within 30 days prior to randomization.
- Patients who require strong or moderate inducers or inhibitors for cytochrome P450, family 3 or subfamily A (CYP3A).

- Patients who have an uncontrolled bleeding disorder or require an anticoagulant (e.g. warfarin or other vitamin K antagonists; novel oral anticoagulants (NOACs) are allowed) at time of screening.

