### **11.3.4 Concomitant Medications**

#### Permitted concomitant medications for both treatment arms

Supportive medications in accordance with standard practice (such as for emesis, diarrhea, etc.) are permitted. Use of granulocyte colony-stimulating factors or erythropoietin growth factors is permitted per institutional policy and in accordance with the ASCO guidelines (Smith 2006), but according the SmPC of Carfilzomib should be used with caution due to the potential risk of thrombosis. Transfusions may be given in accordance with institutional policy. Cotrim as PJP prophylaxis under Carfilzomib treatment is highly recommended. Short courses (≤ 14 days) of steroid treatment for non-WM related medical reasons (e.g. joint inflammation, asthma exacerbation, rash, antiemetic use and infusion reactions) at doses that do not exceed 100 mg per day of prednisone or equivalent are permitted. Cases of venous thromboembolic events, including deep vein thrombosis and pulmonary embolism with fatal outcomes, have been reported in patients who received Carfilzomib. Thromboprophylaxis should be considered based on an individual benefit / risk assessment. The use of these medications / transfusions must be recorded in the eCRF.

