## Concomitant use of antiplatelet agents and anticoagulants

Warfarin or vitamin K antagonists should not be administered concomitantly with Ibrutinib. NOACs are allowed. Supplements such as fish oil and vitamin E preparations should be avoided (patients will be introduced about this in the patient information). Use Ibrutinib with caution in patients requiring other anticoagulants or medications that inhibit platelet function. Patients with congenital bleeding diathesis have not been studied. Ibrutinib should be held at least 3 to 7 days pre- and post-surgery depending upon the type of surgery and the risk of bleeding. Patients requiring the initiation of therapeutic anticoagulation therapy (other than warfarin or a vitamin K antagonist) during the course of the study should have treatment with Ibrutinib held and Ibrutinib should not be restarted until the patient is clinically stable. Patients should be observed closely for signs and symptoms of bleeding. No dose reduction is required when study drug is restarted.

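### Section 11.4.2 suggests warfarin as thromboprophylaxis for patients on Ibrutinib, although section 11.3.4 says it should not be given with Ibrutinib

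*Protocol*

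**What the plan says.** Five places in the protocol bear on this point.

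- **Section 11.4.2, Thromboprophylaxis.** The examples are enteric-coated aspirin, clopidogrel, and then "low molecular weight heparin, or warfarin) is a suggested concomitant medication and should be used with caution in patients on Ibrutinib". The section closes: "Application in patients should be based on an individual benefit risk assessment at the discretion of the investigators".
- **Section 11.3.4, Concomitant use of antiplatelet agents and anticoagulants.** "Warfarin or vitamin K antagonists should not be administered concomitantly with Ibrutinib". The next sentence allows NOACs. Later in the same paragraph, the rule on holding Ibrutinib when anticoagulation is started covers "Patients requiring the initiation of therapeutic anticoagulation therapy (other than warfarin or a vitamin K antagonist) during the course of the study", so vitamin K antagonists are set apart a second time.
- **Section 10.3, Exclusion criteria (repeated in the synopsis).** One criterion covers uncontrolled bleeding disorders and, separately, patients who "require an anticoagulant (e.g. warfarin or other vitamin K antagonists; novel oral anticoagulants (NOACs) are allowed) at time of screening".
- **Section 11.3.4, Permitted concomitant medications for both treatment arms.** After noting fatal venous thromboembolic events reported with Carfilzomib, it says: "Thromboprophylaxis should be considered based on an individual benefit / risk assessment".
- **Section 11.1, Experimental arm.** "If one drug has been discontinued due to toxicities, the other drug can be administered alone in arm A according the protocol". An arm A patient can therefore be on Carfilzomib without Ibrutinib.

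**The concern.** Sections 11.4.2 and 11.3.4 give opposite instructions about the same drug in the same patients. One offers warfarin as a suggestion, subject to caution, for patients on Ibrutinib. The other says it should not be given with Ibrutinib.

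The practical route to harm is short. Section 11.3.4 asks sites to consider thromboprophylaxis because of the thromboembolic risk with Carfilzomib. Section 11.4.2 is the dedicated section, and it stands under the heading *Other Protocol-required Therapies*. An investigator who turns there finds warfarin among the named agents, with no warning that another section advises against it. The risk is bleeding: in its anticoagulant rules, 11.3.4 asks for close observation for bleeding and holds Ibrutinib when therapeutic anticoagulation is started.

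There is also a problem of conduct. The same prescription follows one section and departs from another, so sites and monitors have no consistent basis for classifying it.

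**Working it through.** The protocol gives no figure to reproduce. The check compares the texts.

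**Step 1. Do the two sections address the same patients?**

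| | Section 11.4.2 | Section 11.3.4 (anticoagulants) |
|---|---|---|
| Drug | Warfarin, one of four examples | Warfarin and vitamin K antagonists |
| Patients | Expressly includes those on Ibrutinib | Those on Ibrutinib |
| Instruction | Suggested, with caution, at investigator discretion | Should not be given together |
| Reference to the other section | None | None |

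They do, and the two instructions cannot both be followed by giving warfarin.

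**Step 2. Is there a group for whom 11.4.2 causes no conflict?** Sections 11.1 and 11.3.2.1 let an arm A patient continue Carfilzomib when Ibrutinib is stopped or interrupted. Warfarin given while Ibrutinib is not being taken would not breach 11.3.4. But 11.4.2 is not limited to that situation. Its caution is addressed to patients on Ibrutinib, and both arms are meant to take Ibrutinib until progression or intolerance (section 9.1).

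**Step 3. Which section reflects the protocol's intent?** Section 11.3.4 advises against vitamin K antagonists and leaves them out again in "therapeutic anticoagulation therapy (other than warfarin or a vitamin K antagonist) during the course of the study". The screening exclusion points the same way, with NOACs allowed in both places. Section 11.4.2 is the outlier: it names the oral anticoagulant advised against elsewhere and does not mention NOACs, the class that is allowed.

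**Step 4. How many patients?** The protocol gives no rate of thromboprophylaxis or of warfarin use. Carfilzomib is given only in arm A, where the need mainly arises. With 1:1 allocation of about 99 patients, arm A has 99 / 2 = 49.5 patients. For an **assumed** share given warfarin while on Ibrutinib:

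- 0%: 0 × 49.5 = 0 patients
- 2%: 0.02 × 49.5 = 0.99, about 1 patient
- 5%: 0.05 × 49.5 = 2.475, 2 to 3 patients
- 10%: 0.10 × 49.5 = 4.95, about 5 patients

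These shares have no source in the protocol. They show the scale and are not evidence of risk.

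**The case against.** The strongest defence is that 11.4.2 requires nothing. Warfarin is the last of four examples, use rests on an individual benefit-risk assessment, and 11.3.4 is the more specific rule on anticoagulants with Ibrutinib. Investigators also meet the warfarin exclusion for every patient at screening. A careful site reading both sections would probably follow 11.3.4. This lowers the likelihood of harm. It does not remove the contradiction, because caution and discretion are weaker than an instruction not to give the drug, and could be read as permission to set that instruction aside.

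Three narrower points are fair:

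- The warfarin sentence falls under *Medications to be used with caution*, not under *Prohibited concomitant medications*, and its verb is *should not*. Calling warfarin use a protocol deviation is therefore an inference; the protocol does not say so. The wording is still incompatible with a suggestion to use it, and the placement makes the rule easier to overlook.
- The exclusion criterion concerns need at screening, and the second exception in 11.3.4 concerns therapeutic anticoagulation. Neither governs prophylaxis started later. They show intent, but the contradiction itself rests on one sentence in each of 11.4.2 and 11.3.4.
- The illustrative counts prove nothing about risk and cover arm A only, whereas 11.4.2 has no arm restriction. The conclusion does not depend on them.

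**Conclusion.** The concern holds. Sections 11.4.2 and 11.3.4 contradict each other on warfarin in patients taking Ibrutinib, nothing in the protocol reconciles them, and 11.4.2 is the section out of line with the rest. It is an internal inconsistency with a safety consequence and should be fixed.

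The number of patients exposed cannot be determined from the protocol. It may be zero, and would be about 1 to 5 if 2% to 10% of arm A were given warfarin while on Ibrutinib, shares that are assumed. The finding itself rests only on the protocol's wording. The primary endpoint, the sample size and the analysis are unaffected.

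**What to change.** Delete warfarin from the list in section 11.4.2. This is the cleaner option. If the sponsor wishes to keep it, restrict it explicitly to arm A patients who have permanently stopped Ibrutinib and continue Carfilzomib alone. Permanent cessation is a cautious clinical boundary proposed here; the protocol does not set it.

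In either case, add a sentence to 11.4.2 that vitamin K antagonists are not to be used with Ibrutinib, with a cross-reference to the anticoagulant rules in 11.3.4. The choice among the remaining agents stays with the sponsor's clinicians and the reference safety information.

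The cost is one wording change in 11.4.2 and a short note to sites, with no effect on sample size or analysis.
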